6.5 Safety Analysis Set

The Safety Analysis Set includes all subjects who receive at least one dose of investigational product. For safety analyses during the double-blind period, subjects are summarized according to first study treatment actually received: either UX007 or placebo. Separate listings will capture actual dosing throughout.

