6.6 Extension Analysis Set

The Extension Analysis Set is the subset of subjects in the Safety Analysis Set who continued after the 8 week double-blind placebo-controlled treatment period into the open-label extension period.

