8 STATISTICAL METHODS OF ANALYSIS

8.1 General Principles

During the Double-Blind Placebo-Controlled Treatment Period, efficacy analyses will be based on the Efficacy Analysis Set or the Per Protocol Analysis Set. During the open label period, efficacy analyses will be based on the Extension Set. Safety analyses will be based on the Safety Analysis Set. Unless stated otherwise, statistical tests will be 1-sided hypothesis tests performed at the 5% level of significance and confidence intervals will be 2-sided 90% confidence intervals. Continuous variables will be summarized by number of subjects and mean, standard deviation (SD), median, minimum, and maximum values. Categorical variables will be summarized by number and percentage of subjects.

Analyses and summaries by study period will be done for the following time periods:

- Double-blind placebo-controlled treatment period: after the date of the randomization visit until the date of the week 8 visit
- Open-label extension period: after the date of the week 8 visit until the date of the week 52 visit
- Dose exploration period: after the date of the week 26 visit until the date of the week 36 visit

Overall analyses and summaries will include all subjects and ignore treatment assignment.

For logarithmic transformations of seizure frequency, the natural logarithm will be used and a value of 1 will be added prior to performing the transformation.

For analyses and summaries of subjects while taking UX007, the time while taking placebo will be excluded and the original baseline will be used for all subjects regardless of which treatment was taken during the double-blind placebo-controlled treatment period.

Graphical displays of select study endpoints will be completed and include both observed study data and modeled analyses. Arithmetic means, least square means (LSM), and appropriate measure of dispersion (e.g., standard deviation, standard error) or confidence intervals may be displayed in figures.

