8.7 Safety Analyses

All safety analyses will be based on the Safety Analysis Set. In general safety analyses will be completed using summary statistics, graphs or subject listings. No planned inferential testing of safety endpoints is planned. If after the planned analysis it is determined by the medical writer and study medical monitor that inferential tests of significance may help to provide context for safety information these tests may be performed and identified in the CSR. Summaries will be done by study period and overall.

Analyses and summaries will be performed by study period, by treatment group, for subjects while taking UX007, and overall.

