8.7.1 Adverse Events

Adverse Events will be assessed at all visits and throughout the course of the study. An AE will be considered a treatment emergent adverse event (TEAE) if it occurs or worsens in severity on or after the date of the first dose of study drug. An AE will be considered a UX007 emergent adverse event if it occurs or worsens in severity on or after the first date of

first dose of UX007 during the study. It is expected that the date of first dose of UX007 during the study will be the date of Randomization visit for the UX007 group and the date of Week 8 visit for the placebo group; however, the date of first UX007 dose actually received will be used.

UX007 emergent AEs will be summarized by SOC and preferred term during the period exposed to UX007 by treatment group and overall for all subjects who receive UX007. TEAEs will be summarized by SOC and preferred term during the course of the study by treatment group and overall for all subjects who receive study drug.

Exposure adjusted event incidence, defined as total number of occurrences of an event summed across all subjects in the group divided by the total observed time for events for subjects in the group, will be summarized for TEAEs and UX007 emergent AEs by SOC and preferred term by treatment group and overall.

During the double-blind placebo-controlled period; TEAEs will be summarized by treatment group and overall, and UX007 emergent AEs will be summarized by treatment group and overall. If no placebo subjects also receive UX007 during the double-blind placebo-controlled period, then there will only be one group for UX007 emergent AEs during the double-blind placebo-controlled period. During the open-label extension period, TEAEs and UX007 emergent AEs will both be summarized by treatment group and overall.

A high-level safety summary will display the numbers of subjects who experience one or more AEs in each of the following categories:

- All TEAEs and UX007 emergent AEs
- All treatment related TEAEs and UX007 emergent AEs
- Serious TEAEs and UX007 emergent AEs
- All treatment related SAEs and UX007 emergent SAEs
- Grade 3/4 TEAEs and UX007 emergent AEs
- TEAEs and UX007 emergent AEs leading to study discontinuation
- Fatal TEAEs and UX007 emergent AEs
- TEAEs and UX007 emergent AEs in the GI SMQ (see [Appendix C](#))
- Related TEAEs and UX007 emergent AEs in the GI SMQ

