Table	CANTAB Spatial Working Memory Strategy – Week 8 Analysis – Summary – Efficacy Analysis Set – CANTAB
Table	CANTAB – Change from Baseline – Week 8 Analysis – GEE – Efficacy Analysis Set – CANTAB
Table	CANTAB – Change from Baseline – Week 8 Analysis – GEE – Per Protocol Analysis Set – CANTAB
Table	6MWT Distance (meters) – Week 8 Analysis – Summary – Efficacy Analysis Set – 6MWT
Table	6MWT Distance (percent predicted) – Week 8 Analysis – Summary – Efficacy Analysis Set – 6MWT
Table	Onset of PED – Week 8 Analysis – Summary – Efficacy Analysis Set – 6MWT

Output Type	Title
Table	6MWT – Change from Baseline – Week 8 Analysis – GEE – Efficacy Analysis Set – 6MWT
Table	Onset of PED – Week 8 Analysis – GEE – Efficacy Analysis Set – 6MWT
Table	GMFM-88 Total Score – Week 8 Analysis – Summary – Efficacy Analysis Set – GMFM-88
Table	GMFM-88 Total Score – Change from Baseline – Week 8 Analysis – GEE – Efficacy Analysis Set – GMFM-88
	Exploratory Efficacy Analyses
Table	Frequency of Seizure Types via Diary – Week 8 Analysis – Summary – Efficacy Analysis Set
Table	Frequency of Seizure Types via EEG – Week 8 Analysis – Summary – Efficacy Analysis Set
Table	CGI-S and CGI-I – Week 8 Analysis – Summary – Efficacy Analysis Set – CGI-I
Table	CGI-I – Week 8 Analysis – t-tests – Efficacy Analysis Set
Table	SF-10 – Week 8 Analysis – Summary – Efficacy Analysis Set – SF-10
Table	SF-12 v2 – Week 8 Analysis – Summary – Efficacy Analysis Set – SF-12
Table	SF-10 – Change from Baseline – Week 8 Analysis – t-tests – Efficacy Analysis Set
Table	SF-12 – Change from Baseline – Week 8 Analysis – t-tests – Efficacy Analysis Set
Table	CNS – Week 8 Analysis – Summary – Efficacy Analysis Set – CNS
Table	CNS – Change from Baseline – Week 8 Analysis – t-tests – Efficacy Analysis Set
	Safety Analyses of Adverse Events
Table	Overall Summary of Adverse Events – Safety Analysis Set
Table	Overall Summary of Adverse Events by Study Period – Safety Analysis Set
Table	Treatment Emergent Adverse Events by System Organ Class and Preferred Term – Safety Analysis Set
Table	Serious Treatment Emergent Adverse Events by System Organ Class and Preferred Term – Safety Analysis Set
Table	Treatment Emergent Adverse Events by System Organ Class, Preferred Term and Greatest Severity – Safety Analysis Set
Table	Treatment Emergent Adverse Events by System Organ Class, Preferred Term and Greatest Reported Relationship – Safety Analysis Set

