Table	Grade 3 or 4 Treatment Emergent Adverse Events by System Organ Class and Preferred Term – Safety Analysis Set
Table	Related Treatment Emergent Adverse Events by System Organ Class and Preferred Term – Safety Analysis Set
Table	Gastrointestinal Treatment Emergent Adverse Events by Preferred Term – Safety Analysis Set
Table	UX007 Emergent Adverse Events by System Organ Class and Preferred Term – Safety Analysis Set
Table	Serious UX007 Emergent Adverse Events by System Organ Class and Preferred Term – Safety Analysis Set
Table	Related Serious Treatment Emergent Adverse Events by System Organ Class and Preferred Term – Safety Analysis Set
Table	Related Gastrointestinal Treatment Emergent Adverse Events by Preferred Term – Safety Analysis Set
Table	Treatment Emergent Adverse Events by System Organ Class and Preferred Term (by age group) – Safety Analysis Set

Output Type	Title
Table	Treatment Emergent Adverse Events by System Organ Class and Preferred Term (by gender) – Safety Analysis Set
Table	Treatment Emergent Adverse Events by System Organ Class and Preferred Term (by seizure type) – Safety Analysis Set
Table	Treatment Emergent Adverse Events by Preferred Term – Safety Analysis Set
Table	Serious Treatment Emergent Adverse Events by Preferred Term – Safety Analysis Set
Table	Related Treatment Emergent Adverse Events by Preferred Term – Safety Analysis Set
Table	Exposure Adjusted Treatment Emergent Adverse Event Incidence by System Organ Class and Preferred Term – Safety Analysis Set
Table	Exposure Adjusted UX007 Emergent Adverse Event Incidence by System Organ Class and Preferred Term – Safety Analysis Set
	Safety Analyses of Laboratory and Other Parameters
Table	Chemistry Laboratory Data Summary – Safety Analysis Set
Table	Chemistry Laboratory Shift Table – Safety Analysis Set
Table	Hematology Laboratory Data Summary – Safety Analysis Set
Table	Hematology Laboratory Shift Table – Safety Analysis Set
Table	Urinalysis Laboratory Data Summary – Safety Analysis Set
Table	Urinalysis Laboratory Shift Table – Safety Analysis Set
Table	Chemistry Abnormal and/or Clinically Significant Findings – Safety Analysis Set
Table	Hematology Abnormal and/or Clinically Significant Findings – Safety Analysis Set
Table	Urinalysis Abnormal and/or Clinically Significant Findings – Safety Analysis Set
Table	Vital Signs and Weight Summary – Safety Analysis Set
Table	ECG Results Summary – Safety Analysis Set
Table	ECG Results Shift Table – Safety Analysis Set

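### Open-label adverse-event percentages are assigned to the Safety Analysis Set, so any subject who leaves before Week 8 would dilute them; the subjects who entered the period should be the denominator

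*SAP*

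**What the plan says.** SAP 6.5: "The Safety Analysis Set includes all subjects who receive at least one dose of investigational product". The set therefore keeps subjects who stop before Week 8 or before Week 26.

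SAP 6.6 defines the Extension Analysis Set as "the subset of subjects in the Safety Analysis Set who continued after the 8 week double-blind placebo-controlled treatment period" and moved into open label.

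SAP 8.1 assigns the two sets side by side: "During the open label period, efficacy analyses will be based on the Extension Set. Safety analyses will be based on the Safety Analysis Set". It also lists the study periods, with Dose Exploration (Week 26 to Week 36) among them.

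SAP 8.7 repeats the rule for safety, "All safety analyses will be based on the Safety Analysis Set", and asks for summaries by study period. SAP 8.7.1 adds: "During the open-label extension period, TEAEs and UX007 emergent AEs will both be summarized by treatment group and overall". It also plans the number and percent of subjects with treatment-emergent events by system organ class and preferred term.

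Table 6 in SAP 9 lists "Overall Summary of Adverse Events by Study Period – Safety Analysis Set" and "UX007 Emergent Adverse Events by System Organ Class and Preferred Term – Safety Analysis Set". No safety table carries the Extension Analysis Set.

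**The concern.** A subject who has left the study before a period starts cannot have an event counted in it. Keeping that subject in the denominator lowers the percentage without adding any information about tolerability. The error runs in one direction only, and it grows in later periods as more subjects leave.

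Safety is one of the two primary objectives. Open label runs for 44 of the 52 weeks and is the only UX007 exposure of the former placebo group. If the subjects who tolerate the oil poorly leave early, a full-set denominator makes the remaining period look better tolerated than it was for those who were in it. This matters for Dose Exploration too, since Protocol 7.4.4.1 itself expects tolerability to limit dosing in that range.

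**Working it through.** **What the plan gives.** It states no adverse-event percentage, no by-period denominator and no dropout rate, so there is no figure of the plan's own to reproduce on this point.

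**Inputs from the documents.** About 40 subjects (SAP 3.1), randomized 3:1 (SAP 3.3), so roughly 30 on UX007 and 10 on placebo. SAP 3.3 notes that the first 3 subjects were randomized 1:1, so the split is approximate.

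**Assumptions.** All 40 are dosed. A share d of each arm leaves before the period starts, with d from 0 to 30%. No event of a subject who has left is assigned to the period. The true incidence among entrants is 50%, for illustration.

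**Formula.** Reported % = true % among entrants × (number entering ÷ number in the denominator).

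- Safety Analysis Set as denominator: 40, so the factor is 40(1 − d) ÷ 40 = 1 − d.
- Subjects who ever received UX007 as denominator: 30 + 10(1 − d), because a placebo subject who leaves early never receives UX007.
- Subjects who entered the period as denominator: the factor is 1.

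| d | Entering | Over Safety Analysis Set | Over ever-UX007 | Over entrants |
|---|---|---|---|---|
| 0% | 40 | 40/40 → 50.0% | 40/40 → 50.0% | 50% |
| 5% | 38 | 38/40 → 47.5% | 38/39.5 → 48.1% | 50% |
| 10% | 36 | 36/40 → 45.0% | 36/39 → 46.2% | 50% |
| 20% | 32 | 32/40 → 40.0% | 32/38 → 42.1% | 50% |
| 30% | 28 | 28/40 → 35.0% | 28/37 → 37.8% | 50% |

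In the former placebo column of about 10, one early exit multiplies open-label percentages by 9/10 = 0.90, and two by 8/10 = 0.80.

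**Is the full-set denominator what the text implies?** SAP 8.1 names the Extension Set for open-label efficacy and, in the next sentence, keeps safety on the Safety Analysis Set. SAP 8.7 makes no exception by period, and the by-period adverse-event table is labelled with the same set. A programmer who follows these passages has no other population to use.

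**The case against.** The strongest reply is that naming the population an analysis is based on does not fix the denominator of a by-period percentage. No sentence says that subjects who never entered a period count in its N. That is true. But the Safety Analysis Set is the only population named for safety, and the contrast with efficacy in SAP 8.1 reads as a choice. If the denominator is regarded as open, the same sentence is still needed to close it.

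Second, SAP 3.2 has all 40 subjects entering Dose Exploration, and with no attrition the effect is zero. This stands as a limit on the size. It does not settle the rule. SAP 3.6 allows for withdrawal before Week 8, SAP 8.2 tabulates early discontinuation, and the protocol synopsis (Duration of Treatment) speaks of up to 40 subjects in Dose Exploration.

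Third, SAP 8.7.1 plans exposure-adjusted incidence over observed time, which early leavers do not dilute in this way. That is a real safeguard for UX007 exposure as a whole. However, it is planned by treatment group and for all subjects combined, not by period. Counts and the disposition table would let a careful reader recompute the open-label percentages, but they do not correct what is shown.

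Fourth, the Dose Exploration part is thin. SAP 8.7.1 names only the double-blind and open-label periods, Table 6 lists no Dose Exploration adverse-event table, and the high-level summary is described as showing numbers of subjects. Dose Exploration percentages, and by-period laboratory percentages, follow only from the general by-period wording. This stands, and the point is conditional there.

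Fifth, the periods last 8, 44 and 10 weeks, so raw percentages are not comparable between them whatever the denominator. This also stands; the change proposed here does not cure it.

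**Conclusion.** The point holds for open-label adverse-event percentages by period. Followed literally, the SAP multiplies them by entrants divided by dosed. With assumed attrition of 10% before the period, a true 50% reads 45%; at 20% it reads 40%; at 0% nothing changes. The direction follows from the SAP's text. The size rests entirely on a dropout rate that the documents do not give. The same factor would apply to any Dose Exploration percentages that are produced.

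A reader might go further and infer that placebo subjects who never reach open label stay in the denominator for UX007 emergent events. The documents do not support this: SAP 8.7.1 limits that summary to subjects who receive UX007, and this specific text should govern over the generic set label in Table 6. For the same reason, incidence over the whole UX007 exposure is not understated. What remains is a label that disagrees with the text. UX007-arm subjects who leave early would still dilute an open-label version of that table, as the ever-UX007 column above shows.

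Nor can one say that open-label incidence is in fact understated. The documents support only that it would be, if anyone leaves before the period.

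**What to change.** In SAP 8.7, state that the percentages in by-period safety summaries use the subjects who entered the period: the Extension Analysis Set for open label, and the subjects who started Dose Exploration for any summary of that period. Relabel the by-period safety tables in Table 6 accordingly. Keep the Safety Analysis Set for the double-blind and whole-study tables. Align the Table 6 label for UX007 emergent events with SAP 8.7.1, so that it reads as subjects who receive UX007.

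The cost is a few sentences and some table headers. The Extension Analysis Set already exists, and no new data or analysis method is needed.

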8.7.1 Adverse Events

Adverse Events will be assessed at all visits and throughout the course of the study. An AE will be considered a treatment emergent adverse event (TEAE) if it occurs or worsens in severity on or after the date of the first dose of study drug. An AE will be considered a UX007 emergent adverse event if it occurs or worsens in severity on or after the first date of

first dose of UX007 during the study. It is expected that the date of first dose of UX007 during the study will be the date of Randomization visit for the UX007 group and the date of Week 8 visit for the placebo group; however, the date of first UX007 dose actually received will be used.

UX007 emergent AEs will be summarized by SOC and preferred term during the period exposed to UX007 by treatment group and overall for all subjects who receive UX007. TEAEs will be summarized by SOC and preferred term during the course of the study by treatment group and overall for all subjects who receive study drug.

Exposure adjusted event incidence, defined as total number of occurrences of an event summed across all subjects in the group divided by the total observed time for events for subjects in the group, will be summarized for TEAEs and UX007 emergent AEs by SOC and preferred term by treatment group and overall.

During the double-blind placebo-controlled period; TEAEs will be summarized by treatment group and overall, and UX007 emergent AEs will be summarized by treatment group and overall. If no placebo subjects also receive UX007 during the double-blind placebo-controlled period, then there will only be one group for UX007 emergent AEs during the double-blind placebo-controlled period. During the open-label extension period, TEAEs and UX007 emergent AEs will both be summarized by treatment group and overall.

A high-level safety summary will display the numbers of subjects who experience one or more AEs in each of the following categories:

- All TEAEs and UX007 emergent AEs
- All treatment related TEAEs and UX007 emergent AEs
- Serious TEAEs and UX007 emergent AEs
- All treatment related SAEs and UX007 emergent SAEs
- Grade 3/4 TEAEs and UX007 emergent AEs
- TEAEs and UX007 emergent AEs leading to study discontinuation
- Fatal TEAEs and UX007 emergent AEs
- TEAEs and UX007 emergent AEs in the GI SMQ (see [Appendix C](#))
- Related TEAEs and UX007 emergent AEs in the GI SMQ

Reported AE terms were coded to MedDRA (version 17.1) lowest level terms (LLT) linked to preferred terms (PT) and system organ classes (SOC). The number and percent of subjects with any treatment-emergent adverse events (TEAEs) will be displayed by SOC and PT. Within each level of summarization (SOC or PT), subjects will be counted only once if they had more than one event at that level. The same summary will be performed for TEAEs in

the MedDRA GI SMQ, all related TEAEs, serious TEAEs, those causing discontinuation of investigational product and fatal TEAEs.

The number and percent of subject TEAEs will also be summarized by greatest reported severity grade (AE grading defined in study protocol) for each event preferred term.

The number and percent of subjects experiencing one or more TEAEs for each PT in the GI SMQ will be summarized.

The number and percent of subjects experiencing one or more TEAE, TESAEs, and treatment related TEAEs by descending PT will be summarized.

The number and percent of subjects experiencing one or more TEAE by SOC and PT in order of descending frequency will be summarized by age group (18 and older vs. under 18), gender and seizure type (Observable Seizures Subjects, Absence Seizures Only Subjects).

The number and percent of subjects who withdraw from the study or discontinue study medication due to a TEAE or SAE will be summarized.

The number and percent of subject TEAEs will be summarized by greatest reported relationship (relationship defined in protocol) to study medication.

All TEAEs will be listed individually by subject. In addition, a separate listing will be produced for AEs that are not treatment-emergent. Separate individual subject listings for SAEs and TEAEs leading to Study Withdrawal or discontinuation of Study Medication will also be produced.

8.7.2 Vital Signs and Weight

The following vital signs and weight will be summarized by time point for the observed value and the change from baseline value.

- Temperature (°C)
- Respiration Rate (breaths/min)
- Heart Rate (beats/min)
- Systolic Blood Pressure (mmHg)
- Diastolic Blood Pressure (mmHg)
- Weight (kg)

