Data from nonclinical and clinical studies to date suggest triheptanoin does not pose any serious safety risks that can be identified at this time. Triheptanoin has been well tolerated in humans with no significant safety issues and toxicology or adverse pharmacology findings were not observed in triheptanoin-treated animals. Studies in animals and humans suggest triheptanoin consumed orally has side effects that are similar to those of orally consumed medium chain triglycerides (MCT oil). The most commonly reported adverse effects are gastrointestinal distress and excessive weight gain at high doses. Both of these issues appear to resolve when subjects consume triheptanoin in small doses mixed with foods throughout the day and when total caloric intake is appropriately managed.

Overall the risk-benefit ratio of UX007 is sufficient to support clinical development for the treatment of seizures associated with Glut1 DS.

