**Figure 7.1.1: UX007G-CL201 Study Schema**

## 7.2 Discussion of Study Design, Including Choice of Control Group

The study is a randomized, double-blind, placebo-controlled, parallel-group study to assess the safety and efficacy of UX007 in Glut1 DS. Beginning with the Screening visit, subjects will record their seizure frequency during the 6-week Baseline Period. At the end of the Baseline Period, eligible subjects will be randomized to either UX007 or placebo (3:1 ratio) and begin a 2-week titration schedule to increase dosing until they have reached 35% of total daily calories (~1-4 g/kg/day depending on age). The dose will then be maintained for an additional 6 weeks (total 8-week Treatment Period).

The duration of the Baseline Period and the Treatment Period were designed to: 1) minimize the likelihood of changes to concomitant AED regimens, 2) minimize subject discontinuations due to lack of efficacy since subjects completing the Baseline Period and/or randomized to placebo will not benefit from study drug, and 3) be of sufficient length to allow for accurate determination of the seizure frequencies during those periods.

Ultragenyx has discussed the baseline and treatment period durations with 8 physician expertsPPD

The unanimous advice is that the baseline and treatment periods must be kept to a minimum because the study will enroll a predominantly young pediatric patient population, the majority of whom will likely be under the age of 12 years. This young pediatric population is especially vulnerable to the effects of seizures. The proposed baseline and treatment durations total 14 weeks, and in their opinion is deemed the maximum acceptable duration to them, their patients, and their Institutional Review Boards (IRBs).

Another factor considered in deciding on the duration of the Treatment Period is extent of efficacy over the long term. After the initial 8-week double-blind Treatment Period, the open-label Extension Period will begin, wherein all subjects will be treated with UX007 through Week 52 of the study. Extending the placebo-controlled treatment period is not warranted in this population. Long term safety and maintenance of effect of UX007 will be assessed during this Extension Period. Seizure counts will continue during the Extension Period such that the seizure frequency will be determined over a one-year period, and if warranted, in an additional extension study.

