### 7.3.1 Inclusion Criteria

Individuals eligible to participate in this study must meet all of the following criteria:

- 1) Diagnosis of Glut1 DS confirmed by *SLC2A1* mutation
- 2) Males and females at least 1 year of age at the time of informed consent
- 3) Average of at least 2 observable seizures (generalized or partial-onset [simple partial motor, complex partial, absence, or secondarily generalized] seizures) in 4 weeks over the last 24 weeks, by subject or caregiver report
- 4) At least 2 observable seizures (generalized or partial-onset [simple partial motor, complex partial, or secondarily generalized] seizures) in 4 weeks during the baseline period, with no 3-week seizure-free period during the Baseline Period OR absence seizures documented on Screening EEG
- 5) Continuing to have seizures despite a prior or current use of at least 1 AED
- 6) Allowed to be on up to 3 concomitant AEDs that must have been stable in dose at least 2 weeks prior to the beginning of screening and anticipated to remain stable in dose through the end of the 8-week, placebo-controlled Treatment Period
- 7) Not on, or not fully compliant with a prescribed diet plan (e.g. KD)
- 8) Plasma level of beta-hydroxybutyrate (BHB)  $\leq 1$  mmol/L (non-fasting) at Screening
- 9) Provide written or verbal assent (if possible) and written informed consent by a legally authorized representative after the nature of the study has been explained, and prior to any research-related procedures
- 10) Must, in the opinion of the investigator, be willing and able to complete all aspects of the study, comply with accurate completion of the seizures diary, and likely to complete the 8-week, placebo-controlled, Treatment Period
- 11) Females of childbearing potential must have a negative pregnancy test at Screening, be willing to use an acceptable method of contraception, and have additional

pregnancy tests during the study. Females considered not of childbearing potential include those who have not reached menarche, had total hysterectomy, have been in menopause for at least two years, or have had tubal ligation at least one year prior to Screening.

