#### **7.5.4.2 Vital Signs and Weight**

Vital signs will include seated systolic blood pressure and diastolic blood pressure measured in millimeters of mercury (mm Hg), heart rate in beats per minute, respiration rate in breaths per minute, and temperature in degrees Celsius (°C). Vital signs measurements will be performed at every clinic visit before any additional assessments are completed. At each visit, weight (in kilograms) will be obtained using a scale.

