#### **7.5.4.10 Interim Monitoring Calls**

For additional safety monitoring, the study coordinator will telephone the subject/caregiver between each Extension Period study visit through Week 52. Additional telephone contacts may be made during the Baseline and Treatment Periods as needed. A follow-up call is recommended within 4 weeks following early termination or study completion. The calls will be used to assess AE, discuss any problems or difficulties with treatment, and assess protocol compliance. Study staff will ask about potential adverse effects of study drug including presence of gastrointestinal upset, steatorrhea or frequent loose stools, and weight gain. Staff will inquire about study drug consumption and remaining supply.

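### Weight is summarised only in kilograms across all ages, so outside the 8-week placebo-controlled comparison a mean gain cannot be separated from normal growth

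*SAP*

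**What the plan says.** Protocol 5.3 states the risk: "The most commonly reported adverse effects are gastrointestinal distress and excessive weight gain at high doses". Protocol 7.5.4.10 has staff ask at the monitoring calls about possible adverse effects, "including presence of gastrointestinal upset, steatorrhea or frequent loose stools, and weight gain".

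The population is mostly growing. Inclusion criterion 2 reads "Males and females at least 1 year of age at the time of informed consent", with no upper age limit, and Protocol 7.2 describes a young population, "the majority of whom will likely be under the age of 12 years".

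On measurement, Protocol 7.5.4.2 says "At each visit, weight (in kilograms) will be obtained using a scale". On analysis, SAP 8.7.2 says "The following vital signs and weight will be summarized by time point for the observed value and the change from baseline value", and weight appears in the list that follows in kg. SAP 8.7 sets the grouping: "Analyses and summaries will be performed by study period, by treatment group, for subjects while taking UX007, and overall". It also says "No planned inferential testing of safety endpoints is planned". Table 6 of the SAP plans one summary table and one listing for vital signs and weight.

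Neither document plans a z-score, percentile, percent change, age split or threshold for weight. The split at age 18 in the safety section (SAP 8.7.1) is for treatment-emergent adverse events.

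**The concern.** A growing child gains weight with no drug effect, so a rise in mean weight is expected under the null. How large it is depends on age and puberty. A mean change in kg over toddlers, adolescents and adults adds that rise to any drug effect and weights subjects by absolute size.

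The problem is sharpest in the data most relevant to the named risk. The protocol links weight gain to high doses, and the highest planned level, 40% of calories, is given only in the Dose Exploration Period after Week 26, when every subject is on UX007.

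The two named risks are also treated unequally. Gastrointestinal effects have a dedicated MedDRA query (SAP Appendix C), their own tables and lines in the high-level summary. Weight gain has one line in the vital-signs list, and no weight term is in the query.

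At stake is whether the report can say anything reliable about long-term weight change on UX007. A rise caused by growth could be read as a drug effect, or a drug effect dismissed as growth.

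**Working it through.** There is no stated figure to reproduce: the documents give no expected weight change, SD or threshold for weight. The check compares what each planned summary can remove, then illustrates the size on labelled assumptions.

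**1. What each summary can separate**

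- *Weeks 0-8, by treatment group.* Both groups are randomised and followed for the same time, so average growth cancels in the difference. The comparator is safflower oil at the same dose level and titration (Protocol 7.4.2). The contrast is therefore UX007 against another oil, not against no added oil.
- *Weeks 8-52, by treatment group.* Both groups receive UX007. The difference between them reflects at most the 8 extra weeks of earlier exposure. Within each group, growth remains in the mean.
- *On UX007.* There is no comparator. SAP 8.1 keeps the original baseline for everyone, so for subjects first on placebo the change also includes 8 weeks of growth on placebo oil.
- *Overall.* Treatment assignment is ignored, so growth remains.

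**2. Precision of the one controlled contrast**

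About 40 subjects at 3:1 gives about 30 and 10. (The first 3 were randomised 1:1, which hardly alters this.) The 90% CI half-width for a difference in mean change is t(0.95, 38 df) × SD × √(1/30 + 1/10) = 1.686 × SD × 0.365 = 0.616 × SD. The SD of 8-week change is assumed to be 0.5 to 2 kg:

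- SD 0.5 kg: half-width 0.31 kg
- SD 1 kg: 0.62 kg
- SD 2 kg: 1.23 kg

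**3. Growth left in the uncontrolled period**

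Assume normal growth of g = 1 to 5 kg per year in children. Expected gain with no drug effect is g × weeks/52:

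| Growth (kg/year) | 8 weeks | 44 weeks | 52 weeks |
|---|---|---|---|
| 1 | 0.15 | 0.85 | 1 |
| 3 | 0.46 | 2.54 | 3 |
| 5 | 0.77 | 4.23 | 5 |

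If adults are assumed not to change and 60% to 90% of subjects are growing, the pooled 52-week mean with no drug effect runs from 0.6 × 1 = 0.6 kg to 0.9 × 5 = 4.5 kg.

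**4. Pooling in kilograms**

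The same 2 kg is 2/10 = 20% of body weight in a 10 kg child and 2/70 = 2.9% in a 70 kg adult.

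**5. Whether better data are available**

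Protocol 7.5.4.1 collects date of birth and sex, and 7.5.4.2 collects weight. A weight-for-age z-score needs nothing more. The SAP already adjusts for age, sex and height in the 6-minute walk test under age 20 (SAP 5.8.2).

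**The case against.** A reader might infer that the plan cannot detect or exclude drug-related weight gain at all. The documents do not support that, for three reasons.

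- *There is a controlled contrast.* In Weeks 0-8 the by-group summary against randomised placebo allows for average growth. This stands. It is small, short and against another oil, and no test is planned.
- *There is an adverse-event route.* Monitoring calls ask about weight gain. Clinically significant change in weight is a listed safety endpoint (SAP 4.4). Reported events are tabulated by preferred term, severity, relationship and age group, and as exposure-adjusted incidence (SAP 8.7.1). An investigator can judge a child against expected growth. This also stands, but no criterion is given, and the list in Protocol 7.5.4.9 of changes to be recorded as adverse events does not name weight.
- *Individual data are shown.* The listing gives each subject's weights, and SAP 8.1 adds median, minimum and maximum. The pooled summary is therefore hard to interpret rather than empty.

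Three further arguments deserve weight. Protocol 5.3 adds that the effect appears to resolve with small doses taken with food and managed calorie intake, and the trial includes dietitian review. That bears on how likely the effect is, not on whether the summary can show it. Safety analysis in this Phase 2 study is descriptive, and z-scores could be derived later from the same data. That limits the harm, but a prespecified summary is more credible than one added after the data are seen. Finally, a z-score does not supply a control: in the extension a change in z could still reflect diet or disease. It removes expected growth, which is the largest predictable component, and no more.

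**Conclusion.** The point holds for the 44 of 52 weeks without placebo, and for the on-UX007 and overall summaries. There, the mean change in kg mixes normal growth with any drug effect, and the plan has no means to separate them. It does not hold for the by-group comparison in Weeks 0-8, where growth cancels on average and the limits are about 10 placebo subjects and the oil comparator.

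The size is illustrative. Growth of 1 to 5 kg per year, a 60% to 90% share of growing subjects and no change in adults are assumptions, not document figures. The direction needs only that children grow. A reader might also infer that growth is as large as the excess gain of interest. The documents define no such gain, so that comparison cannot be made. No efficacy conclusion is affected. The change should be made because the risk is named in the protocol and the remedy is cheap.

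**What to change.** In SAP 8.7.2:

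1. For paediatric subjects within the age range of a named growth reference, add the change from baseline in age- and sex-standardised weight z-score, by treatment group to Week 8 and by visit to Week 52.
2. Show weight separately for under 18 and 18+, matching the split in SAP 8.7.1. Keep kg for adults and for listings.
3. For on-UX007 summaries, also show change from the last weight before the first UX007 dose. State the weeks on UX007 beside it: at Week 52 these are about 44 for subjects first on placebo and 52 for the others.
4. If a count of subjects with excessive gain is wanted, the sponsor should define the cut-off in advance. The documents offer none, and none is proposed here.

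The cost is a reference lookup and one extra table, with no new data collection. A BMI z-score would need height, which the SAP uses for the walk test but Protocol 7.5.4.2 does not schedule, so weight-for-age is the simpler choice.
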